## 5.0 BACKGROUND AND RATIONALE

### 5.1 Rationale

Influenza infection is known to be associated with increased risk of cardiovascular (CV) events. Several lines of investigation suggest that influenza vaccine might attenuate cardiac risk in high-risk populations. However, influenza vaccine is widely and profoundly underutilized in this population. Our meta-analysis of randomized controlled trials (RCTs) suggests the use of influenza vaccine compared with placebo or routine care in high-risk patients is associated with a lower risk of major adverse cardiovascular events (MACE) (2.9% vs. 4.7%; risk ratio [RR] 0.64, 95% CI, 0.48-0.86; P=0.003). Five key observations from this analysis and our mechanistic work form the rationale to proceed with a definitive randomized, controlled trial to extend these findings: (1) a treatment interaction detected between patients with (RR 0.45, 95% CI, 0.32-0.63) and without (RR 0.94, 95% CI, 0.55-1.61) a recent acute coronary syndrome (P-interaction=0.02) suggests that higher risk cardiovascular patients derive the greatest cardioprotective benefit from influenza vaccine; (2) further reduction in MACE was suggested in RCTs of more potent versus standard influenza vaccine (RR 0.72, 95% CI, 0.46-1.13); (3) patients with advanced heart disease in the form of heart failure (HF) who contract influenza are at significantly greater risk for acute HF and CV hospitalizations during winter months compared with similar high-risk patients without influenza infection; (4) evidence from our lab and others indicates that patients with HF have reduced influenza antibody titers and altered cytokine production following influenza vaccination (immunosenescence), and that this reduction is related to the severity of underlying heart disease; and (5) our pilot RCT suggests that immunosenescence in patients with advanced heart disease may be overcome with higher-dose influenza vaccine.

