## 9.0 STUDY PROCEDURES

### 9.1 Screening/Baseline Visit

- Obtain written informed consent and medical release of information form
- Review medical records for past medical history (including recent hospitalization and previous influenza vaccinations) and current medications (will be also be assessed annually if enrolled)
- Reconfirm eligibility (if baseline visit is on a later date than the screening visit)
- Collect medical history, social history, baseline questionnaires (i.e frailty survey; NYHA/CCS functional status), demographics and contact information for follow-up, including the patient's social security number (US only) or provincial health insurance number (for Canada only)- when permissible according to local ethics regulations, the names and contact information of two family members or friends that could be contacted if the subject is unreachable
  - For participants with documented evidence of adult congenital heart disease (ACHD) participating in the correlative ACHD substudy, additional medical and surgical history will be collected.
- Review medical records for height, weight, and temperature (if available)
- Patients must not be given study vaccination prior to Randomization
- Blood will be drawn for baseline measurement of antibody titers and other biomarkers in a subset of consenting subjects
- Randomize subject via the internet using the Statistical Registration and Randomization System
  - The StaRRS randomization software will return a treatment code corresponding to either high-dose or standard-dose vaccine
  - Labels containing the treatment allocation code will be on the drug packet. Verify correct assignment.
- Dispense and administer vaccine (all efforts should be made to vaccinate same day as randomization)
- Monitor subject for at least 20 minutes post vaccination for injection site and allergic reactions
- Dispense 7 day AE diary with instructions for reporting recorded information at the one week follow up phone call
- Provide a proof of vaccination letter to those who may require it
- Schedule one-week follow-up contact

#### 9.1.2 PATIENTS RETURNING FOR YEAR 2 AND 3

- Review medical records for past medical history (including recent hospitalization and previous influenza vaccinations) and current medications
- Confirm that the patient does not meet exclusion criteria

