### **13.7 Analysis of Immune Outcomes (Correlative Study Endpoints)**

Antibody titers and other immune responses such as the incidence of seroconversion and seroprotection in A/H1N1, A/H3N2 and B-type vaccine antigens will be summarized with descriptive statistics such as mean and standard deviation or median and IQR for quantitative measures and frequency and proportion for qualitative measures for baseline and week 4 post-vaccination along with graphics such as bar plots and compared between the two treatment arms using two-sample tests. Clinical outcomes will be compared between those with and those without seroconversion and seroprotection in A/H1N1, A/H3N2 and B-type vaccine antigens using log-rank tests. Cox proportional hazards regression analysis will be performed for the primary endpoint of the composite of all-cause death or cardiopulmonary hospitalization with the geometric mean titer across vaccine strains post-vaccination as a model term, instead of individual antibody titers, to avoid issues of collinearity, stratified by influenza season, while adjusting for other covariates including treatment and other immune responses and the interaction between treatment and match for circulating B (Victoria)-lineage that is included only in the standard-dose QIV (binary), based on influenza typing and subtyping data. The hazard ratio for each doubling of the geometric mean titer will be estimated along with confidence intervals from Cox proportional hazards regression models. Given that the traditional definition of seroprotection, namely HAI titers  $\geq 40$ , may be an inadequate estimate of a protective threshold during years of poor match between vaccine antigens and circulating strains, we will also assess seroprotection defined as HAI  $\geq 80$ , 160, and 320 as exploratory analyses.

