2.3. Correlative Study Objectives for the Immune Response Substudy

- 2.3.1. To test the hypothesis that a higher influenza vaccine dose will result in more pronounced humoral immune response, evidenced by greater mean titers post-vaccination and higher antibody titer changes from baseline
- 2.3.2. To test the hypothesis that higher antibody concentrations will be associated with a reduced rate of the composite of all-cause death and cardiopulmonary hospitalization

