8.6 Analysis of the Correlative Endpoints for the Immune Response Substudy

Antibody titers at baseline and week 4, change in antibody titers from baseline to week 4, and the incidence of seroconversion and seroprotection in A/H1N1, A/H3N2 and B-type vaccine antigens and in A/H1N1, A/H3NW and B-Yamagata lineage at 4 weeks following vaccinations will be summarized with descriptive statistics such as geometric mean and standard deviation or median and IQR for quantitative measures and frequency and proportion for qualitative measures along with graphics such as box plots or empirical distribution functions and bar plots and compared between the two treatment arms using two-sample tests with robust variance to account for intra-subject correlation over multiple vaccinations.

Clinical outcomes will be compared between those with and those without overall seroconversion and seroprotection and antigen-specific seroconversion and seroprotection to A/H1N1, A/H3N2, B-Yamagata and B-Victoria vaccine antigens (for standard dose vaccine) and to A/H1N1, A/H3N2 and B-Victoria lineage (for high dose) using log-rank

tests. Cox proportional hazards regression analysis will be performed for the primary endpoint of the composite of all-cause death or cardiopulmonary hospitalization with the geometric mean titer across vaccine strains post-vaccination as a model term, instead of individual antibody titers, to avoid issues of collinearity, stratified by enrolling season, while adjusting for other covariates including treatment and other immune responses and the interaction between treatment and match for circulating B-Yamagata lineage that is included only in the standard-dose QIV (binary), based on influenza typing and subtyping data. The hazard ratio for each doubling of the geometric mean titer will be estimated along with confidence intervals from Cox proportional hazards regression analysis with robust variance estimation. Given that the traditional definition of seroprotection, namely HAI titers ≥ 40 , may be an inadequate estimate of a protective threshold during years of poor match between vaccine antigens and circulating strains, we will also assess seroprotection defined as HAI ≥ 80 , 160, and 320 as exploratory analyses.

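### Clinical outcomes are compared by serostatus with log-rank tests that state no adjustment, although serostatus is not randomized and the protocol ties weaker response in heart failure to disease severity

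*SAP*

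**What the plan says.** SAP 8.6 sets out three analyses that relate antibody to clinical outcome.

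- **Serostatus.** "Clinical outcomes will be compared between those with and those without overall seroconversion and seroprotection", and likewise for antigen-specific response, by log-rank test. Protocol 13.7 has the same plan: "Clinical outcomes will be compared between those with and those without seroconversion and seroprotection in A/H1N1, A/H3N2 and B-type vaccine antigens using log-rank tests". Neither sentence gives a stratification factor, a covariate or a variance correction.
- **Titer, Cox model.** The exposure enters "with the geometric mean titer across vaccine strains post-vaccination as a model term". The model is stratified by enrolling season and fitted "while adjusting for other covariates including treatment and other immune responses", plus the interaction of treatment with B-lineage match. Robust variance is stated.
- **Titer, count model.** Hospital days per month are regressed on log titer, controlling for treatment and further covariates that are not named.

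The hypothesis served is SAP objective 2.3.2, that "higher antibody concentrations will be associated with a reduced rate of the composite of all-cause death and cardiopulmonary hospitalization". In its rationale (5.1), the protocol says of the reduced antibody titers in heart failure that "this reduction is related to the severity of underlying heart disease". SAP 8.11 calls any non-primary two-sided p-value below 0.05 significant, with the number of comparisons noted.

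**The concern.** Subjects are not randomized to respond to a vaccine. If sicker hearts respond less well, as Protocol 5.1 says for heart failure, and if sicker patients also die or are admitted more often, then non-responders will have more events even when antibody does nothing. A crude log-rank test cannot tell this from protection.

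SAP 8.8 recognises that baseline characteristics such as age, AMI versus HF and renal dysfunction are prognostic or possible confounders, but uses them only for treatment subgroups.

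Seroconversion has a second difficulty. It is a fourfold rise from baseline (SAP 4.4.3), and a high starting titer makes that rise harder to reach. Non-seroconverters therefore mix true non-responders with people who may already have been protected.

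At stake is the reading of objective 2.3.2: a difference in case mix could be reported as a significant antibody-outcome association.

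**Working it through.** **Is the missing adjustment a real feature of the plan?** In SAP 8.6 the sentence after the log-rank tests gives the titer Cox model its season stratification and covariates. The between-arm titer comparisons and the titer hazard ratio each get robust variance. The serostatus tests get none of these. Reading them as unadjusted is an inference from silence, but from silence beside explicit specification.

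**Do the design inputs hold?** The documents give no power or sample size for the serostatus comparison, so only the main-trial figures can be reproduced. With 1,296 events and HR 0.82: √(1296/4) × |ln 0.82| = 18 × 0.1985 = 3.572. Power is Φ(3.572 − 1.96) = 0.947, or Φ(3.572 − 1.98) = 0.944 with the final boundary, against 0.943 stated. The planned event rates and counts are not in dispute.

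**Inputs for the illustration.**

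- From the documents: at most 3,000 subjects, about 1,000 per post-Vanguard season (Protocol 12.0); a 9% first-season event rate (Protocol 13.12, SAP 7); two-sided 0.05 (SAP 8.11).
- Assumed, because the documents give no figure: half are responders; severity is a continuous score that multiplies the hazard by 1.3 or 1.5 per SD and the odds of response by 0.7 or 0.8 per SD; antibody has no effect.

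**Apparent hazard ratio**, responders against non-responders, by simulation with exponential event times, administrative censoring and an unadjusted two-group log-rank test:

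- hazard 1.5, response odds 0.7: HR 0.87
- hazard 1.5, response odds 0.8: HR 0.92
- hazard 1.3, response odds 0.8: HR 0.95
- no effect of severity on hazard: HR 1.00, with 5% rejections

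**Chance of p < 0.05.** Let E be the number of events and d = √(E × 0.5 × 0.5) × |ln HR|. The chance is Φ(d − 1.96) + Φ(−d − 1.96). For HR 0.87 and 3,000 subject-seasons, E = 0.09 × 3,000 = 270 and d = 8.216 × 0.1393 = 1.144, so the chance is Φ(−0.816) + Φ(−3.104) = 0.207 + 0.001 = 0.21. The same formula gives:

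| Subject-seasons (events) | HR 0.87 | HR 0.92 | HR 0.95 |
|---|---|---|---|
| 3,000 (270) | 21% | 11% | 7% |
| 2,000 (180) | 15% | 9% | 6% |
| 1,000 (90) | 10% | 7% | 6% |

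At 3,000 the simulated rates were 20%, 11% and 7%, in agreement.

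The smaller sizes are shown because 3,000 is a ceiling. SAP 6 puts the ITT data cut-off at July 31, 2019, which would leave two post-Vanguard seasons, while SAP 8.10 still lists 2019-2020. A flat 9% also ignores the planned 8% and 7% in later seasons.

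**Check by a second route.** Split severity into two classes with hazard ratio H, and let s_r and s_n be the severe shares among responders and non-responders. The apparent HR is (1 − s_r + s_r·H)/(1 − s_n + s_n·H). With 40% against 60% severe and H = 2 this is 1.4/1.6 = 0.875. With 240 to 270 events and 50% to 70% responders, the chance of p < 0.05 is 16% to 20%.

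**What the scenarios leave out.** They assume that antibody does nothing, so they omit the opposite push from subjects already protected by a high starting titer. They describe severity confounding only, not the net bias for seroconversion.

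**The case against.** The case on the other side is substantial.

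- **Objective 2.3.2 already has adjusted analyses.** It concerns antibody concentration, and the titer Cox and count models match it. Their open covariate wording could admit severity. This stands, and it rules out a tempting stronger reading: that the trial tests antibody against outcome only by crude comparison. What remains is that no severity covariate is named in advance and that neither model analyses serostatus.
- **Treatment arm may be handled.** SAP 8.6 lists the antigens for the antigen-specific tests separately for standard-dose and high-dose vaccine, which can be read as within-arm comparison. A reader should not infer that those tests certainly pool the arms.
- **General statements may reach these tests.** Protocol 13.18.2 speaks of post-stratifying the analysis by age, AMI versus HF and season, and SAP 8.1 calls for robust variance under the mITT approach. Neither is tied to the serostatus tests. The SAP does not repeat the first, and its own primary analysis stratifies by season alone. Neither covers functional class, frailty or baseline titer.
- **Direction.** One might infer that the plan must overstate protection. That follows for severity confounding alone. For seroconversion the starting titer can act in the opposite direction.
- **Size.** Starker contrasts give more alarming figures. With 30% against 60% severe and H = 3, the second formula gives 1.6/2.2 = 0.73 and a chance of p < 0.05 of 62% to 74%. Nothing in the documents supports so strong a contrast. The statement in Protocol 5.1 is about heart failure, whereas entry is also possible on MI alone.
- **Consequence.** The substudy is optional and correlative, its hypothesis is worded as an association, and SAP 8.11 requires the number of comparisons to be noted. That limits the harm. It does not make an association that planned adjustment might remove informative about antibody.

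**Conclusion.** The concern holds within limits. Followed as written, the plan tests a non-randomized grouping without adjustment for a confounder that the protocol itself names, and SAP 8.11 lets the result be called significant. The adjusted titer models reduce the damage but do not cure it.

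Under the assumed links, with no antibody effect and 1,000 to 3,000 subject-seasons, the apparent hazard ratio is about 0.87 to 0.95 and the false-positive rate about 6% to 20% instead of 5%. These figures are illustrative: the severity hazard ratio, the severity-response link and the responder share are all assumptions. They show how severity acts and do not estimate the bias to expect. For seroconversion the net direction is not established.

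A reader might infer that the efficacy conclusion is at risk. It is not: the primary randomized comparison, its type I error and the between-arm comparison of titers do not depend on these tests. This is worth correcting in the SAP, but it is a matter for the correlative objective only.

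**What to change.** In SAP 8.6:

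1. Test seroconversion and seroprotection in Cox models stratified by enrolling season and arm, with robust variance because subjects may take part in several years (Protocol 9.3.1). Adjust for a pre-specified list: age group, AMI versus HF, NYHA/CCS class, frailty, prior vaccination and log pre-vaccination titer.
2. Name the same severity and baseline-titer covariates in the planned Cox model for geometric mean titer.
3. Keep Kaplan-Meier curves and log-rank results by serostatus, labelled unadjusted and descriptive.

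No new data are needed. Protocol 9.1 already collects "baseline questionnaires (i.e frailty survey; NYHA/CCS functional status", with medical history and previous influenza vaccinations, and substudy subjects give a baseline sample for titers. The cost is SAP wording and a few degrees of freedom. Adjustment deals with measured severity only. Residual confounding by unmeasured factors will remain and should be acknowledged when the results are reported.

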8.7 Analysis of Exploratory Efficacy Endpoints

Analysis of the exploratory efficacy endpoint in 4.5.1, time to first occurrence of cardiovascular death or heart failure hospitalization, subject to competing risk of death other than cardiovascular death, within each enrolling season, will be performed using standard method for competing risk with robust variance as in Section 8.5.1.

Analysis of the exploratory efficacy endpoint in 4.5.2, time to first occurrence of cardiovascular death, non-fatal MI, or non-fatal stroke, subject to competing risk of death other than cardiovascular death, within each enrolling season, will be performed using standard method for competing risk with robust variance, also as in Section 8.5.1.

Analysis of the exploratory efficacy endpoint in 4.5.3, time to first occurrence of all-cause death or pulmonary hospitalization within each enrolling season will be performed using standard method with robust variance as in Section 8.3 for the primary efficacy endpoint.

8.8 Subgroup Analysis

Many baseline characteristics are known to be prognostic or suspected to be confounders for the clinical outcomes in the study population with high-risk cardiovascular disease. They include age, sex, race/ethnicity, smoking status, obesity (BMI \geq 30), baseline CV risk group (AMI vs HF), diabetes, renal dysfunction, and use of statin and beta-blocker medications. Influenza season is also known to affect the clinical outcome. Internal consistency of the primary analysis will be assessed in subgroups defined by these and other baseline characteristics. Heterogeneity of efficacy will be assessed using interaction

tests of treatment by each of these baseline covariates and by influenza season. Any interaction test resulting in a heterogeneity p-value < 0.10 will be further evaluated for clinical plausibility of effect modification.

8.9 Analysis of Safety Endpoints

The analysis of the safety endpoints will follow the mITT analysis used for the primary efficacy endpoints. The primary safety endpoint is incidence of vaccine injection site reactions such as injection site reactions (e.g. erythema, pain, or redness), and systemic side effects including headache, myalgia, and fever. The number and percentage of subjects experiencing vaccine injection site reactions will be summarized by treatment arm and by enrolling season, and the incidence will be compared using nonparametric methods such as chi-square tests. Incidence of vaccine injection site over multiple seasons will be considered independent.

The secondary safety endpoint is incidence of vaccine-related adverse events and serious adverse events and will be analyzed as above for the primary safety endpoint.

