### **13.18 Measures to Minimize/Avoid Bias**

#### **13.18.1 Randomization**

Randomization will be carried out using permuted blocks of random block size, stratified naturally by influenza season, balanced by clinical site. Subjects will be randomized in a 1:1 ratio to high-dose or standard-dose vaccine. Subjects will remain on the same dose for subsequent influenza sessions. The clock is reset to zero each year for every subject, whether or not he or she continues with the study. That means that subsequent events are counted in the primary analysis only for persons who continue with the study, i.e., who are revaccinated per their original assignment. It also means that a person can contribute a new event to the primary endpoint for each year of participation in the trial. The trial will therefore employ a modified intention-to-treat (mITT) analysis in which subjects' clocks will be reset 2 weeks after influenza vaccination, and primary endpoint events will be counted until July 31 of that year. Events that occur after that point in persons who do not get revaccinated are unlikely to be related to the original vaccination. Although a subject's experiences from year to year may be correlated, for simplicity, each subject's contribution for each influenza season will be treated as independent.

Subjects will be randomized using Frontier Science and Technology Research Foundation's web-based the Statistical Registration and Randomization System (StaRRS) that is available 24/7 and only accessible to designated site personnel. StaRRS will confirm subject eligibility in a stepwise fashion as each protocol defined eligibility criteria is verified. Only when a subject meets all protocol-defined eligibility requirements will the system provide a randomization code in a blinded manner. A notification of successful randomization will appear within the application and will also be sent via e-mail to the clinical site. Detailed instructions can be found in the Statistical Registration and Randomization User Manuel.

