5. ANALYSIS SETS

With vaccination at enrollment into each influenza season and because the effects of vaccination last at least a calendar year, there will be no typical adherence issues. However, we expect some subjects will not be re-vaccinated according to randomization in subsequent influenza seasons. We will therefore employ a modified intention-to-treat (mITT) analysis in which events of interest will be analyzed per vaccination for each enrolling season, and primary endpoint events accrue from 2 weeks after influenza vaccination until July 31 of each enrolling season. Each subject can therefore contribute primary endpoint events and other endpoint events in multiple seasons in which they are vaccinated. As a subject's experiences from year to year may be correlated, each subject's contribution for each enrolling season may be considered correlated.

All subjects randomized will comprise the intent-to-treat (ITT) population. The usual ITT principle for analysis of randomized controlled trials will be followed for the assessment of balance in baseline data at randomization and for analysis of secondary efficacy endpoints 4.2.1, total (first and recurrent) cardiopulmonary hospitalizations or all-cause death across all enrolling seasons, and 4.2.3, time to first occurrence of all-cause death or cardiopulmonary hospitalization across all enrolling seasons.

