8. STATISTICAL METHODS

8.1 General Principles

All statistical data analyses will be performed using SAS (SAS Institute, Inc., Cary NC) and R (R Foundation for Statistical Computing, Vienna, Austria. <http://www.R-project.org>).

Analyses of efficacy and safety endpoints will employ the mITT analysis as described in Section 5, except for the analysis of baseline data and the secondary efficacy endpoints in 4.2.1, total (first recurrent) cardiopulmonary hospitalizations or all-cause death across all enrolling seasons, and in 4.2.3, time to first occurrence of all-cause death or cardiopulmonary hospitalization, both across all enrolling reason, which will employ the ITT analysis.

With the mITT analysis to efficacy and safety analysis, each subject will potentially contribute endpoints more than once over multiple influenza seasons, and endpoints in each subject may be correlated. In order to account for the intra-subject correlation over multiple influenza seasons, a robust variance estimator will be used in statistical inference. Due to the randomization-once strategy, those returning for re-vaccination following the initial vaccination after randomization constitute non-random cohorts. This may introduce bias due to potential differential survivorship and drop-out after the initial randomization.

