8.3 Analysis of the Primary Efficacy Endpoint

8.3.1. Primary efficacy analysis

The primary efficacy analysis will be performed on the primary endpoint of the time to first occurrence of all-cause death or cardiopulmonary hospitalization within each enrolling season according to the mITT analysis described above in Section 6. All randomized unique patients who received vaccinations at the beginning of enrolling seasons are included. If a patient does not return for re-vaccination for a subsequent season as per the randomization-once strategy, that patient is not included for that or any subsequent enrolling seasons. Each patient can contribute events in multiple consecutive seasons in which they are vaccinated. The event accrual period will begin 2 weeks following receipt

of influenza vaccine and continue until summer phone call (July 31st) follow-up with the time to first event as elapsed time from vaccination.

The primary efficacy analysis will be based on a two-sided log-rank test with robust variance at a significance level of 0.05, stratified by enrolling season. The Kaplan-Meier method will be used to estimate the survival distribution for the time to first event for the composite of all-cause death or cardiopulmonary hospitalization. An unadjusted estimate of the hazard ratio and confidence interval will be obtained using a Cox proportional hazards model with only treatment as a model term, stratified by enrolling season (Cox, 1972) with robust variance estimation (Wei, Lin and Weissfeld, 1989).

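### SAP 8.9 treats a subject's safety outcomes in different seasons as independent, against SAP 8.1; a safety test pooled over seasons would give p-values that are too small if the outcomes are positively correlated

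*SAP*

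**What the plan says.** SAP 8.9 puts the safety endpoints on the per-vaccination mITT basis used for primary efficacy. It summarizes injection site reactions by arm and season and compares incidence with tests such as chi-square. It then states: "Incidence of vaccine injection site over multiple seasons will be considered independent". The secondary safety endpoint, vaccine-related and serious adverse events, "will be analyzed as above for the primary safety endpoint". Whether each test is run within a season or over all seasons together is not stated.

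The rest of the SAP takes the other view of repeat seasons:

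- SAP 8.1: "With the mITT analysis to efficacy and safety analysis, each subject will potentially contribute endpoints more than once over multiple influenza seasons". It goes on to say that these outcomes may be correlated and that, for this reason, "a robust variance estimator will be used in statistical inference".
- SAP 5: "each subject's contribution for each enrolling season may be considered correlated".
- SAP 8.3.1, the analysis that 8.9 says it follows: "two-sided log-rank test with robust variance at a significance level of 0.05".
- SAP 8.6, for the immune endpoints: "two-sample tests with robust variance to account for intra-subject correlation over multiple vaccinations".

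Protocol 13.18.1 fixes the arm within subject: "Subjects will remain on the same dose for subsequent influenza sessions".

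A separate wording point lies in the same section. One sentence of 8.9 lists systemic symptoms (fever, headache, myalgia) under the primary safety endpoint. SAP 4.3.1, protocol 10.4.1 and the next sentence of 8.9 count injection site reactions only, and protocol 11.4.4 lists the systemic symptoms separately.

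**The concern.** A subject who reacts to the vaccine in one season may well be more likely to react in the next. Arm is constant within subject, so such correlation does not cancel in the arm contrast; it adds to its variance. A chi-square test that counts each vaccination as a new, independent person uses too small a standard error.

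Under SAP 8.11 any other two-sided p below 0.05 is called statistically significant, so the size of these tests matters for what is reported. Two analysts, one following 8.1 and one following 8.9, could report different p-values from the same data. SAP 9 has two teams of statisticians validate all analyses, so the conflict would have to be settled at that stage if not before.

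**Working it through.** **1. Inputs (SAP 7, protocol 13.12, SAP 3).** New subjects: 500, then 2,933 in each of three seasons, together 9,299. At most three seasons each. Not revaccinated: 30% per later season (20% and 40% as variants). Event rates 9%, 8% and 7% in a subject's first, second and third season, with 30% of events being deaths. Two-sided 0.05. The within-subject correlation (ICC) is **not in the documents**; 0.1, 0.3 and 0.5 are assumed.

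**2. Reproducing the plan's own figure.** Return after a first season is 0.70 × (1 − 0.30 × 0.09) = 0.6811, and after a second 0.70 × (1 − 0.30 × 0.08) = 0.6832. Vaccinations per season are then 500; 3,274; 5,163; 6,295. Applying 9/8/7% gives 45.0, 291.2, 440.1 and 519.3 events, total 1,295.6. The plan states 45, 291, 440 and 519, total 1,296, so this is the repeat-vaccination structure that the plan assumes.

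**3. Vaccinations per subject (m).** The Vanguard and 2017-2018 cohorts (3,433 subjects) can have three, the 2018-2019 cohort two, and the 2019-2020 cohort one.

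- m = 3: 3,433 × 0.6811 × 0.6832 = 1,597
- m = 2: 3,433 × 0.6811 × 0.3168 + 2,933 × 0.6811 = 2,738
- m = 1: the remaining 4,963
- Σm = 15,232 (rounded to whole vaccinations) and Σm²/Σm = 1.989

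**4. Variance inflation.** With arm fixed within subject and a common ICC, the variance of the pooled arm difference is the independence variance times

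Deff = 1 + ICC × (Σm²/Σm − 1) = 1 + 0.989 × ICC.

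**5. True size of the nominal 0.05 test:** 2 × [1 − Φ(1.96/√Deff)].

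| ICC | Deff | SE understated by | True size | Correct p of 0.05 is reported as |
|---|---|---|---|---|
| 0 | 1.00 | 0% | 0.050 | 0.050 |
| 0.1 | 1.10 | 5% | 0.062 | 0.040 |
| 0.3 | 1.30 | 12% | 0.085 | 0.026 |
| 0.5 | 1.49 | 18% | 0.109 | 0.017 |

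At ICC 0.3, non-return of 20% or 40% gives factors 1.117 or 0.855 and size 0.090 or 0.080.

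**6. Shorter follow-up.** SAP 6 names a July 31, 2019 cut-off, but only under the ITT analysis. If it also governed safety, 6,366 subjects would have 8,937 vaccinations (4,028, 2,106 and 233 subjects with one, two and three), the factor would be 0.627, and the size 0.057, 0.072 and 0.087 at ICC 0.1, 0.3 and 0.5. At ICC 0.3, non-return of 20% or 40% gives 0.075 or 0.069.

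**7. Simulation check under the null.** Beta-binomial outcomes, same arm each season, pooled chi-square.

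- 20,000 trials at an assumed incidence of 0.30 gave 0.062, 0.087 and 0.106 (full plan) and 0.060, 0.071 and 0.091 (2019 cut-off) at ICC 0.1, 0.3 and 0.5.
- 3,000 trials at incidences of 5% and 30% (full plan) gave 0.049 to 0.055 at ICC 0, 0.075 to 0.082 at 0.3, and 0.106 to 0.119 at 0.5. The Monte Carlo standard error near 0.085 is √(0.085 × 0.915/3,000) = 0.005, so these agree with the formula to about two standard errors.
- A Cochran-Mantel-Haenszel test stratified by season gave nearly the same rejection rates as the unstratified test. Stratifying by season alone is therefore no cure.
- Tests within a single season stayed at 0.048 to 0.055.

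**The case against.** The strongest reply is that no pooled safety test is specified. The second listed change in SAP 1.3 bases safety on each vaccination season, SAP 4.3 defines both safety endpoints within season, and 8.9 summarizes by season. On that reading each subject enters each test once, the size is nominal, and the sentence does nothing. This limits the point: the figures above apply only if person-seasons are combined. It does not remove it. An independence assumption across seasons has a use only when seasons are combined, so the sentence itself suggests pooling. If pooling is not meant, the sentence is idle and still conflicts with 8.1.

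It can also be said that 8.9 is the specific section and may be an exception to a general principle, and that protocol 13.2 treated seasons as independent for simplicity. But 8.1 names safety, 8.9 gives no reason for an exception, and SAP 5 and 8.1 moved away from the protocol's simplification. The wording of SAP 5 is permissive, so the firm conflict is with 8.1.

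Three further points stand as limits:

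- The ICC is unknown, may differ between local reactions and serious events, and gives only a small error near 0.1. The calculation also takes non-return as unrelated to reactions, although an adverse reaction is a listed reason to discontinue.
- For injection site reactions, protocol 5.4 already reports more local symptoms at the higher dose, so a false rejection there has little practical weight. It matters more for serious adverse events.
- Too-small p-values flag harm too readily rather than hide it. Even so, a confidence interval built on the same variance would be too narrow.

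**Conclusion.** The concern holds. SAP 8.9 states an independence rule that contradicts SAP 8.1, and the rule reaches both safety endpoints. Applied to a comparison pooled over seasons, it gives a true size of about 0.06 to 0.11 for a nominal 0.05 test under the full plan and 0.057 to 0.087 under the 2019 cut-off, for assumed ICCs of 0.1 to 0.5. There is no error at ICC 0. The direction follows from the randomize-once design and needs only positive correlation; the size rests on the assumed ICC and the plan's own return rates. By-season tests and primary efficacy are sound on this point, and under protocol 13.19 no formal stopping boundary uses the safety tests. The systemic-symptom wording is a minor, separate slip and adds nothing to this conclusion.

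**What to change.** Delete the independence sentence in SAP 8.9 and replace it with text to this effect, applied to the primary and secondary safety endpoints alike:

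> Arms will be compared by chi-square within each enrolling season. Any comparison pooled over seasons will be stratified by enrolling season and will use a robust variance clustered on subject, in line with Section 8.1 (for example, GEE with season as a factor).

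Stating that safety is tested by season only would also resolve the conflict.

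Separately, limit the primary safety sentence in 8.9 to local reactions as protocol 11.4.4 defines them, and report fever, headache, malaise and myalgia under the secondary vaccine-related adverse event endpoint.

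The cost is SAP wording and standard code, with no new data. With positive correlation, pooled safety p-values become somewhat larger; by-season results and primary efficacy do not change.
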